3.2. Schedule of Activities

This section includes the following SoA:

- Screening, Treatment, and Post-Discontinuation Follow-Up SoA for all participants
- Continued-Access SoA for participants on abemaciclib (See Section 7.8.1 of the CAMPFIRE Master Protocol for additional details)

Overview

The windows for the SoA and administration of first dose are based on calendar days.

At any time in the study, laboratory and pregnancy tests may be collected at a local clinic in accordance with local laws and regulations if deemed appropriate by the investigator. All results should be reviewed and recorded in the eCRF. A virtual visit with the study investigator is not required for a local lab draw or pregnancy test.

Screening and Baseline

The screening period allows up to 28 days for confirmation of eligibility and completion of baseline assessments.

Treatment Period

Cycles are 21 days. During the on-study treatment period, participants will return to clinic on Days 1-5 for IV infusions. Additional evaluations on Day 8 and Day 15 of each cycle will be conducted on-site, remotely (that is, by telephone, IT-assisted virtual visit, mobile healthcare, or a combination thereof) or a combination of remote and on-site at the direction of the sponsor, according to local laws and regulations.

Treatment will continue until disease progression, unacceptable treatment-related toxicity, or participant or physician decision to discontinue.

Tumor Response

Tumor response per RECIST 1.1 should be assessed approximately every 2 cycles (at Cycles 3 and 5) and then every 3 cycles (beginning Cycle 8) until the participant has objective disease progression, death, or study completion.

Short- and Long-Term Follow-Up

Participants discontinuing study intervention will return for a short-term follow-up visit (Visit 801). The short-term follow-up visit will take place 30 days (± 14 days) after the decision is made to discontinue all study treatment.

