After the short-term follow-up visit, all participants will enter the long-term follow-up period (Visit 802-8XX). Long-term follow-up begins the day after the short-term follow-up visit is completed and continues until participant's death, withdrawal from study, or study completion. Long-term follow-up visits should occur approximately every 2-3 months (Q60-90D). Tumor assessments should continue approximately every 3 months during follow-up for participants without evidence of disease progression at the time of treatment discontinuation.

Table JP04.1. Baseline Schedule of Activities

Procedure	Day relative to C1D1		Instructions
	≤28	≤14	
Informed consent	X		
 Must be signed prior to conducting any protocol-specific tests/procedures Minor participants must be re-consented if they reach the age of majority during the course of the study.
Inclusion/exclusion criteria	X		
 Confirm prior to randomization
Randomization	X		
Demographics	X		
 Include race, gender, ethnicity, and birth date per local regulations.
Preexisting conditions and medical history, including relevant surgical history	X		
 Include Ewing's sarcoma or Ewing's sarcoma-like fusion genes, if known CCI
Prior and current treatments for Ewing's sarcoma	X		
 Record prior anticancer therapy
Substance use (alcohol and tobacco)	X		
Concomitant medications	X		
 Record all premedication, supportive care, and concomitant medication See Section 3.7.6
Adverse events	X		
 CTCAE Version 5.0
Height, weight, and body surface area	X		
Vital signs	X		
 Temperature, blood pressure, pulse rate, and respiratory rate
Physical examination	X		
 Includes respiratory auscultation
CCI	X		
 CCI
Performance status	X		
 Lansky for age <16 years Karnofsky for age ≥16 years

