3.5.1.1. Criteria to Begin Day 1 of Subsequent Cycles (C2 and beyond)

CCI	

Treatment may be suspended for a maximum of 21 days to allow a participant sufficient time for recovery from study treatment-related toxicity. In exceptional circumstances, a delay >21 days is permitted upon agreement by Lilly CRP/CRS.

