3.7. Treatments

3.7.1. Treatments Administered

Table JP04.6 shows the treatment regimens.

Table JP04.6. Treatment Regimens

Starting Doses Cycle = 21 days				
	Abemaciclib PO		Irinotecan IV (Days 1-5 each cycle)	Temozolomide PO (Days 1-5 each cycle)
	<18 years	≥18 years		
Arm A	55 mg/m ² BID (max dose 100 mg BID)	100 mg BID	50 mg/m ² /day × 5	100 mg/m ² /day × 5
Arm B	None		50 mg/m ² /day × 5	100 mg/m ² /day × 5
Authorized as defined by EU Clinical Trial Regulation	Authorized and not used according to EU authorization		Authorized and not used according to EU authorization	Authorized and not used according to EU authorization

Abbreviations: BID = twice daily; IV = intravenous; PO = orally.

Participants will begin dosing-assigned treatment on Cycle 1 Day 1. A cycle is defined as an interval of 21 days timed to irinotecan and temozolomide. The 21-day cycle, anchored to irinotecan and temozolomide, should be maintained throughout the treatment phase. Cycles may not be less than 21 days.

When delays are required, doses should be resumed at the earliest medically appropriate opportunity based on investigator judgment and dose adjustment guidelines (Section 3.7.8).

Treatment will continue until progression, unacceptable toxicity, or other discontinuation criteria are met (Section 3.8).

A delay to the start of a cycle of a dose due to holiday, weekend, weather, or other unforeseen circumstances will be permitted for a maximum of 7 days and not counted as a protocol deviation. In exceptional circumstances, a delay of >7 days is permitted upon agreement between the investigator and the Lilly CRP/CRS. Abemaciclib treatment may continue during the delay if there is sufficient drug supply and if there are no toxicities that would prevent treatment.

Irinotecan and temozolomide must be administered on 5 consecutive days.

Packaging and labeling

Treatments administered in the study will be supplied by the sponsor in accordance with current Good Manufacturing Practice. Study interventions will be labeled as appropriate for country requirements.

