3.7.8.2. Discontinuation of One Study Treatment

Participants may discontinue irinotecan and/or temozolomide (due to chemotherapy-associated toxicities) while continuing abemaciclib upon discussion with the Lilly CRP/CRS. If abemaciclib must be discontinued, participants may continue to receive irinotecan and/or temozolomide. For all study drugs, if dose reductions are required beyond the lowest dose, the drug should be discontinued. Continuation on chemotherapy beyond Cycle 12 will be up to the investigator's discretion and the individual participant's situation. Prior to continuing the participant on chemotherapy beyond Cycle 12, the investigator should discuss with the Lilly CRP/CRS. Abemaciclib may continue beyond Cycle 12 until discontinuation criteria is met.

Dose Modification for Neutropenia						
Note: For hematologic toxicities, dose holds, and reductions - apply simultaneously to all drugs as indicated						
	Abemaciclib		Irinotecan		Temozolomide	
Severity and Duration	Dose Hold	Dose Reduction	Dose Hold	Dose Reduction	Dose Hold	Dose Reduction
Grade 3	Recommend G-CSF in subsequent cycle					
Grade 4 Initial incident	Hold until ANC CCI	Consider 1 dose level reduction. If already taking G-CSF, reduce 1 dose level.	Hold until ANC CCI	Reduce 1 dose level	Hold until ANC CCI	No reduction Recommend G-CSF in subsequent cycle
Grade 4 >7 days duration or >14-day cycle delay		Reduce 1 dose level Recommend G-CSF in subsequent cycle		Recommend G-CSF in subsequent cycle		Reduce 1 dose level Recommend G-CSF in subsequent cycle
Grade 4 Recurrent ^a						Reduce 1 dose level Recommend G-CSF in subsequent cycle
Dose Modification for Febrile Neutropenia						
Note: For hematologic toxicities, dose holds, and reductions - apply simultaneously to all drugs as indicated						
Grade 3 Initial incident	Hold until resolution	Consider 1 dose level reduction Recommend G-CSF in subsequent cycle	Hold until resolution	Consider 1 dose level reduction Recommend G-CSF in subsequent cycle	No change	
Grade 3 Recurrent ^a				Reduce 1 dose level Recommend G-CSF in subsequent cycle		
Grade 4				Reduce 1 dose level Recommend G-CSF in subsequent cycle		Reduce 1 dose level if not previously on G-CSF Reduce 2 dose levels if G-CSF was used Recommend G-CSF in subsequent cycle

Abbreviations: ANC = absolute neutrophil count; G-CSF = granulocyte-colony stimulating factor.

Grade 3: ANC < 1000/mm³; **Grade 4:** ANC < 500/mm³.

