7.7. Efficacy Analyses

7.7.1. Primary Outcome and Methodology

7.7.1.1. Definition

The primary endpoint of this study is progression-free survival by blinded, independent, review committee (PFS by BIRC). PFS is defined as the time from randomization until the first occurrence of documented disease progression per RECIST 1.1 criteria, or death from any cause in the absence of progressive disease, whichever comes first. A secondary endpoint will also consider documented disease progression as determined by investigator assessment, as described in Section 7.7.1.7. Participants known to be alive and without disease progression will be censored at the time of the last adequate tumor assessment (a detailed PFS event/censoring scheme is provided in Table JP04.7.1).

Table JP04.7.1. PFS Event/Censoring Scheme

Situation	Event/Censor	Date of Event or Censor
Tumor progression or death	Event	Earliest date of PD or death
No tumor progression and no death	Censored	Date of last adequate tumor assessment, per RECIST 1.1 criteria, or date of randomization (whichever is later) ^b
Unless		
No baseline radiologic tumor assessment available	Censored	Date of randomization

Situation	Event/Censor	Date of Event or Censor
No adequate postbaseline tumor assessment available and death reported after 2 scan intervals following randomization ^b	Censored	Date of randomization
Tumor progression or death documented immediately after 2 or more scan intervals following last adequate tumor assessment or randomization (whichever is later) ^{a,b}	Censored	Date of last adequate tumor assessment, per RECIST 1.1 criteria, or date of randomization (whichever is later) ^a

Abbreviations: CR = complete response; PD = progressive disease; PFS = progression-free survival; PR = partial response; RECIST 1.1 = Response Evaluation Criteria in Solid Tumors, Version 1.1; SD = stable disease.

- ^a Adequate tumor assessment per RECIST 1.1 criteria refers to an assessment with 1 of the following responses CR, PR, SD, or PD.
- ^b Following the schedule of activities in the protocol, scans should be performed approximately every 2 cycles through Cycle 5, then approximately every 3 cycles until objective disease progression, death, or study completion.

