7.7.1.5. Additional Analyses of PFS

In addition to the primary analysis of PFS using the Bayesian hierarchical analysis described above, traditional (frequentist) assessments will be performed to provide additional context. The Kaplan-Meier (KM) method (Kaplan and Meier 1958) will be used to estimate the rPFS curves as well as rPFS rates at 3, 6, 9, and 12 months for each treatment group. The corresponding HR between treatment groups will be estimated using a stratified Cox regression model (Cox 1972), stratified by the randomization strata. An additional unstratified Cox regression model will be employed to explore the effects of the stratification variables on treatment response.

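### On-treatment scans follow cycle number while PFS runs from randomization, so unequal delays or stopping times could date progression differently by arm; fixing imaging by weeks from randomization is a cheap improvement.

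*Protocol*

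**What the plan says.** **On treatment.** Protocol 3.2 (Tumor Response) says response "should be assessed approximately every 2 cycles (at Cycles 3 and 5) and then every 3 cycles (beginning Cycle 8". SAP 7.7.1.1, footnote b to the censoring table, repeats this: "Following the schedule of activities in the protocol, scans should be performed approximately every 2 cycles through Cycle 5", then about every 3 cycles. Neither place gives days or weeks.

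**Cycle length.** Protocol 3.7.1: "A cycle is defined as an interval of 21 days timed to irinotecan and temozolomide" and "Cycles may not be less than 21 days". The same section allows a cycle to start up to 7 days late for logistical reasons. Section 3.5.1.1 adds: "Treatment may be suspended for a maximum of 21 days to allow a participant sufficient time for recovery". Both limits can be exceeded by agreement with the sponsor.

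**After treatment.** Protocol 3.2 (Short- and Long-Term Follow-Up): "Tumor assessments should continue approximately every 3 months during follow-up" for those who stopped without progression. Table JP04.3 instead gives 60-90 days and lets the Visit 801 scan be skipped if the last scan was under 90 days earlier. Section 3.7.8.2 leaves chemotherapy beyond Cycle 12 to the investigator after discussion with the sponsor, and says "Abemaciclib may continue beyond Cycle 12 until discontinuation criteria is met".

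**Endpoint.** PFS counts from randomization (Protocol 3.10.3.1.1; SAP 7.7.1.1). The SAP also reports "rPFS rates at 3, 6, 9, and 12 months for each treatment group" (7.7.1.5).

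**The concern.** The endpoint clock starts at randomization, but the on-treatment imaging clock advances only as cycles are given. No legible rule keeps a scan on its date when a cycle slips. An arm with more delay would be scanned later, and its progressions would be recorded later.

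The arms could plausibly differ in two ways:

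- Protocol 3.3.3 names overlapping toxicity of the three drugs, including Grade 3-4 neutropenia and thrombocytopenia, as the main risk. Only Arm A receives all three, so its cycles may slip more. This would favor Arm A.
- After chemotherapy ends, Arm A can stay on abemaciclib and on 9-week scans, while Arm B has no study drug left and moves to follow-up scans. If those are sparser, this favors Arm B.

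Blinded review protects how a scan is read, not when it was taken. None of the three sensitivity analyses in SAP 7.7.1.8 (stratification covariates, other priors, no borrowing) addresses scan timing. Protocol Table JP04.7 leaves the length of two scan intervals to the SAP, which gives only the cycle schedule, so that censoring rule has no fixed length in days.

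**Working it through.** The plan's own power figure cannot be reproduced, because events, HR, alpha and power are redacted. What can be checked is how far scan dates move and what that does to an HR that is truly 1.0.

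**Step 1. Scan days.** A scan at Cycle k with cycle length L falls on day (k - 1) x L from C1D1.

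| Scan at | L = 21 | L = 24 | L = 28 |
|---|---|---|---|
| Cycle 3 | 42 | 48 | 56 |
| Cycle 5 | 84 | 96 | 112 |
| Cycle 8 | 147 | 168 | 196 |
| Cycle 11 | 210 | 240 | 280 |
| Cycle 14 | 273 | 312 | 364 |

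A mean delay of 7 days per cycle makes these scans 14, 28, 49, 70 and 91 days late. A mean delay of 3 days makes them 6, 12, 21, 30 and 39 days late.

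**Step 2. More delay in Arm A.** Assumptions: true HR 1.0; exponential PFS with median 3-7 months; every progression dated to the next scheduled scan; Arm A cycles of 24-28 days against 21 in Arm B; cut-off at 540 days; equal arm sizes. The exponential HR is the ratio of (events / follow-up time). The Cox-type HR is the Mantel-Haenszel ratio, sum(dA x nB / n) / sum(dB x nA / n).

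- Exponential: 0.95-0.99
- Cox-type: 0.89-0.97

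The Cox-type figure is the less stable. Weighting the same calculation 2:1 moves it further below 1. In simulated trials of 30 against 15 participants under several assumed delay patterns (medians 3-6 months), the Cox HR was mostly 0.91-0.99, with Monte Carlo error about 0.02. In those trials the log-rank false-positive rate, at a nominal one-sided 5%, was 7-11% with random delays and varying scan days, and 10-20% if every Arm A cycle slipped equally. An exponential Wald test without borrowing stayed at 3-6%. With the same schedule in both arms, the HR was 1.00 and the log-rank rate 4.8-6.4%.

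**Step 3. Arm B leaving treatment.** Same model, 21-day cycles in both arms, all of Arm B off treatment after Cycle 12, Arm A staying on 63-day scans.

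| Arm B follow-up interval | Apparent HR |
|---|---|
| 63 days | 1.00 |
| 75 days | 1.01-1.03 |
| 90 days | 1.03-1.05 exponential, 1.04-1.06 Cox-type |

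**Step 4. Both together.** With Arm A cycles of 24-28 days and 90-day follow-up scans in Arm B, the exponential HR is 0.97-1.05 and the Cox-type HR 0.91-1.06, on either side of 1.

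**Step 5. Scale.** If all 45 participants (30 and 15) had events, the SE of the log HR would be sqrt(1/30 + 1/15) = 0.32. The exponential shift in Step 2 is |ln 0.99| = 0.01 to |ln 0.95| = 0.05, or about 0.03 to 0.16 SE.

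**Step 6. Landmark rates.** Three months is day 91, against a nominal scan on day 84; nine months is day 274, against day 273. With median 5 months (152 days), the recorded rate is 2^(-t/152), where t is the last scan before the landmark. On nominal days, t = 84 gives 68% and t = 273 gives 29%. With scans 8 days later, t = 50 gives 80% and t = 218 gives 37%. The jumps of 12 and 8 points are worst cases: they need every scan on its exact day and C1D1 equal to randomization.

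**The case against.** **The governing text may be lost.** The imaging row of Table JP04.2 is not legible in the supplied text, and a scan window or an instruction to hold scan dates could sit there. Protocol 3.7.1 also asks that the 21-day cycle be maintained, and 3.2 says only approximately every 2 cycles. This stands, and makes the point conditional on checking that row.

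**Unequal delay is assumed.** No rates by arm are given. G-CSF is permitted in both arms (3.7.4.4), and the triplet was tolerable in the Phase 1b study (3.3.3). A mean 28-day cycle means a week's slip every cycle in Arm A and none in Arm B. This also stands.

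**The Arm B mechanism is weak.** Section 3.7.8.2 does not stop chemotherapy at Cycle 12, and 60-90 days includes the 63-day on-treatment interval. Only the 90-day end with complete stopping gives 1.03-1.06.

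**The model overstates the effect.** Deaths count on their own date, and Table JP04.3 calls for a scan within 4-6 weeks of stopping for clinical progression. Both dilute the shifts.

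**The landmark rates are supportive only.** A two-day gap between randomization and C1D1 moves the day-273 scan past nine months in both arms. With an assumed gap of 0-7 days and scan days varying by 3-7 days, the same 8-day shift changes the 9-month rate by about 1 point and the 3-month rate by 5-9 points. The 6- and 12-month rates already lie mid-interval.

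A reader might infer that open-label treatment causes the problem. It does not: delay-driven scan timing would operate under blinding too.

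What survives is structural: no legible passage ties on-treatment imaging to the clock that PFS uses.

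**Conclusion.** The point holds as a cheap improvement. Scan dates can differ by arm for reasons unrelated to disease, and blinded review cannot repair that. Under the stated assumptions, the shift from delay is 1-5% of the HR in an exponential model, the form of the primary likelihood. Without borrowing, that is small beside the sampling error. It is larger, 0.89-0.97, in Cox-type analyses, which matter for the frequentist futility look and the supportive estimates.

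A reader might conclude that detected PFS will differ between arms, that the design favors abemaciclib, or that the primary test is invalid. The documents support none of these. There are no delay or stopping rates by arm, the two mechanisms oppose each other with an unknown net direction, and the full primary model and priors are redacted, so its error rate cannot be computed.

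**What to change.** In Protocol 3.2, Tables JP04.2 and JP04.3, and SAP footnote b, schedule imaging in both arms by time from randomization at the present nominal spacing: weeks 6, 12, 21, 30, then every 9 weeks, with a stated window. Keep it regardless of cycle delay, dose hold or end of treatment, until objective progression. Reconcile the 3-month and 60-90-day follow-up statements, and state two scan intervals in days to match. First confirm what the imaging row of Table JP04.2 says.

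Optionally, report PFS rates at mid-interval times, since the 3- and 9-month rates sit close to nominal scan dates.

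The cost is an amendment of wording. Some scans will fall away from Day 1 visits, the first may come before two cycles are complete when C1D1 lags randomization, and some off-treatment scans will come earlier than now.

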- Treatment will continue until disease progression, unacceptable treatment-related toxicity, or participant or physician decision to discontinue.
- Participants discontinuing study intervention will return for a short-term follow-up visit (Visit 801) 30 days (± 14 days) after discontinuation of all study treatments.
- Long-term follow-up begins the day after the short-term follow-up visit and continues until participant's death, withdrawal from study, or study completion. Long-term follow-up visits should occur approximately every 2-3 months (Q60-90D). For participants without disease progression at treatment discontinuation, tumor assessments should occur approximately every 3 months.

Study Population:

Participants have Ewing's sarcoma or Ewing's sarcoma-like tumor that has not responded to previous treatment or has returned, are 1 to <40 years old, are ≥ 10 kg, and have a life expectancy of at least 8 weeks. Participants must be able to swallow and/or have a gastric/nasogastric tube. If on systemic steroids at study entry, the dose must be stable or decreasing during the 7 days prior to Cycle 1 Day 1.

Intervention Groups and Duration:

All participants will come to the investigative site on Day 1 to 5 of each 21-day cycle to receive:

- Irinotecan IV infusion
- Temozolomide capsules

Arm A participants will also take abemaciclib orally twice daily during each 21-day cycle.

Additional evaluations on Day 8 and Day 15 of each cycle will be conducted either at the study site, remotely (that is, by telephone, IT-assisted virtual visit, mobile healthcare, or a combination thereof) at the direction of the sponsor, according to local laws and regulations.

Ethical Considerations of Benefit/Risk:

[figure not shown]
The safety and efficacy profile for combination of abemaciclib, irinotecan, and temozolomide supports the overall benefit/risk profile. This combination was tolerable in Part A of Study JPCS in pediatric participants with relapsed or refractory solid tumors. Considering the measures to minimize risk, including frequent assessments by the medical team including monitoring of

hematologic and hepatic laboratory values, and the potential benefit of disease control, the benefit/risk profile is considered favorable for this patient population.

Data Monitoring Committee: Yes (Independent DMC).

Overall Design:

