PK samples	See Attachment 3 for sampling schedule															See Section 3.9.4 and Attachment 2 for sample collection guidance	
Exploratory biomarkers (plasma, whole blood)	See Attachment 3 for sampling schedule															
Predose (C1D1) and at disease progression or time of study treatment discontinuationSee Attachment 2 for sample collection guidance	
Administer irinotecan	See Notes															Administer on Days 1-5 of each cycle	
Administer temozolomide	See Notes															
Administer on-site prior to irinotecan infusion on Days 1-5 of each cycleIf irinotecan is omitted, on-site visit is not required on Days 2-5	
Dispense	See Notes															Arm A only: PO BID per Section 3.7.1	

Procedure	All Treatment Periods (Cycle = 21 Days)															Notes
	Cycle 1			Cycle 2			Cycle 3			Cycle 4			Cycle 5-n			
Relative Day within Dosing Cycle	1	8	15	1	8	15	1	8	15	1	8	15	1	8	15	
abemaciclib																
Participant returns study drugs				X			X			X			X			Return at Day 1 of each cycle to assess compliance (± 5 days)

Abbreviations: BID = twice daily; BSA = body surface area; C = cycle; CBC = complete blood count; CTCAE = Common Terminology Criteria for Adverse Events (NCI 2017); D = day; CCI [REDACTED]; IV = intravenous; CCI [REDACTED]; CCI [REDACTED]; PO = orally; PK = pharmacokinetics; RECIST 1.1 = Response Evaluation Criteria in Solid Tumors, Version 1.1 (Eisenhauer et al. 2009).

- ^a Virtual or remote visits, potentially partnered with a Home Health Service may be leveraged for participants when deemed appropriate by the investigator and allowed by local laws and regulations.
- ^b Home health service may be leveraged to collect and process laboratory samples prior to or during a participant's visit (on-site or virtual/remote). Must be allowed by local laws and regulations.

Table JP04.3. Poststudy-Treatment Follow-Up Schedule of Activities

	Short-Term Follow-Up ^a	Long-Term Follow-Up ^d	
Visit	801	802-8XX	
Visit Interval Tolerance (Days)	CCI		
Procedure			Instructions
Concomitant medication	X ^b		
AE collection	X ^b	X	
 CTCAE Version 5.0 After Visit 801, only study treatment-related serious events are reported
Survival information	X	X	

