Serum pregnancy: Confirmation only needed if urine test is positive. 1 mL estimated and displayed in table, regardless of WOCBP status for participants ≥10 years of age.

CCI

Visit 801:

- Has visit interval tolerance of ±14 days.

Exploratory biomarker collected only for participants who did not have a sample collected at the time of disease progression or at the time when study treatment was discontinued, additional 10 mL for participants ≥10 years of age.

Potential triggered collections:

Hepatic monitoring triggered for safety reasons with a range of 1.8 mL to 76.3 mL.

Cystatin C triggered for safety reasons, additional 2.5 mL.

Disease Progression: Exploratory biomarker collection, additional 10 mL for participants ≥10 years of age.

Retests, as needed, PK an additional 0.01 to 4 mL.

Reference

[EU] Ethical considerations for clinical trials on medicinal products conducted with minors. Recommendations of the expert group on clinical trials for the implementation of Regulation (EU) No 536/2014 on clinical trials on medicinal products for human use. Rev. 1. Published September 18, 2017. Accessed August 10, 2022.

https://www.ejprarediseases.org/wp-content/uploads/2021/10/EC_ethical-consideration-on-clinical-trials-with-minors_2017.pdf

Spain

This addendum is to address feedback from the Agencia Española de Medicamentos y Productos Sanitarios (AEMPS) in Spain.

The revised text in the following sections shows the changes applicable only to participants in Spain. All deletions have been identified by ~~strikethroughs~~; all additions have been identified by the use of underscore.

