7.1.2. Handling of Dropouts and Missing Data

Baseline will refer to the last nonmissing observation before first administration of any treatment unless stated otherwise. Missing data, except for dates, will not be imputed. When dates are used in calculations, missing days will be replaced with 15th of the month and missing day/month

with 01 JULY. Where windows are allowed for data collection and there is more than 1 reading in any window, appropriate consideration will be given as to whether only 1 value from the window should be used, and if so how it should be chosen. This could either be the mean (geometric mean) or the value closest to the mid-point of the window or the value closest to the data collection time of another variable if the analysis involves time-matched analyses.

Detailed censoring rules for evaluation of the primary PFS endpoint are provided in [Table JP04.7.1](#).

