7.9.2. Adverse Events

The MedDRA Version 21.0 (or higher) will be used to map reported AEs to MedDRA terms. The MedDRA LLT will be used in the treatment-emergent computation. PTs identified as clinically identical or synonymous may be grouped together under a single consolidated PT. For

example, ‘Neutropenia’ and ‘Neutrophil count decreased’ may be aggregated and reported as ‘Neutropenia.’ The NCI CTCAE version 5.0 will serve as the reference document for grading the severity of all AEs and other symptoms.

Pre-existing conditions are defined as AEs that begin prior to the first dose of study treatment.

A TEAE is defined as any AE that begins between the day of first dose and 30 days after treatment discontinuation (or up to any time if serious and related to study treatment), or any preexisting condition that increases in CTCAE grade between the day of first dose and 30 days after treatment discontinuation (or up to any time if serious and related to study treatment). Comparisons of preexisting conditions to on-treatment events at the LLT level will be used in the treatment-emergent computation.

A SAE is any AE during this study that results in one of the following outcomes: death, initial or prolonged inpatient hospitalization, a life-threatening experience (that is, immediate risk of dying), persistent or significant disability/incapacity, congenital anomaly/birth defect, or considered significant by the investigator for any other reason. Additionally, important medical events that may not result in death, be life-threatening, or require hospitalization may be considered SAEs when, based on appropriate medical judgment, they may jeopardize the patient and may require medical or surgical intervention to prevent 1 of the outcomes listed in this definition.

Treatment-emergent adverse events will be summarized by SOC and by decreasing frequency of PT within SOC.

Safety analyses will include summaries of the following:

- AEs, including severity and possible relationship to study drug
- SAEs, including possible relationship to study drug
- AEs leading to dose adjustments
- discontinuations from study treatment due to AEs or death
- treatment-emergent abnormal changes in laboratory values
- treatment-emergent abnormal changes in vital signs.

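### Full AE collection can stop up to 14 days before the 30-day TEAE window ends, and the mid-month date rule misclassifies AE onsets in the month of first dose

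*Protocol*

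**What the plan says.** **Visit 801 and AE reporting.** The Protocol Synopsis (3.1) places the short-term follow-up visit "30 days (± 14 days) after discontinuation of all study treatments". The text of Protocol 3.2 uses a different starting point: "The short-term follow-up visit will take place 30 days (± 14 days) after the decision is made to discontinue all study treatment". The tolerance cell in Table JP04.3 is redacted, but the country sections for Germany and Spain in Attachment 9 give the same tolerance: "Has visit interval tolerance of ±14 days". On AE collection, Table JP04.3 states "After Visit 801, only study treatment-related serious events are reported". The next period is tied to the visit and not to a calendar day: "Long-term follow-up begins the day after the short-term follow-up visit is completed".

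**TEAE window.** SAP 7.9.2 states "A TEAE is defined as any AE that begins between the day of first dose and 30 days after treatment discontinuation". The restriction to serious, related events applies only after that window. AEs that start before first dose are pre-existing conditions, and they become TEAEs only if their CTCAE grade rises.

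**Partial dates.** SAP 7.1.2 says that "missing days will be replaced with 15th of the month and missing day/month" become 1 July. It makes no exception for AE onset or for death.

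**The concern.** The collection rule and the analysis rule do not cover the same days. The SAP promises a count of all AEs to Day 30, but the case report form may stop asking for most of them from Day 16. Events that were never recorded cannot be recovered at analysis. Table JP04.3 schedules hematology and chemistry at Visit 801 but not in long-term follow-up, so laboratory data do not fill the gap.

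The date rule is a separate weakness in the same tables. Whether an AE counts as treatment-emergent should depend on whether it began before or after first dose. For an onset with the day missing in the month of first dose, it depends instead on whether first dose fell before or after mid-month. Applied to a death, the rule can produce an impossible survival time.

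Safety of the combination is the first-listed secondary objective. With 45 participants randomized 2:1, Arm B has 45 × 1/3 = 15, so one misclassified or unrecorded participant moves an Arm B incidence by 1/15 = 6.7 percentage points.

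**Working it through.** The plan gives no figure of its own to reproduce here.

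**1. Collection window against TEAE window**

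Inputs: Visit 801 at 30 ± 14 days (Protocol 3.1, 3.2, Attachment 9); restricted reporting after it (Table JP04.3); TEAE window to Day 30 (SAP 7.9.2).

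Visit range: 30 − 14 = Day 16 to 30 + 14 = Day 44. Days without full collection = max(0, 30 − visit day), if both clocks start on the same day:

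- visit on Day 16: 30 − 16 = 14 days (14/30 = 47%)
- visit on Day 23: 30 − 23 = 7 days (7/30 = 23%)
- visit on Day 30 or later: 0 days

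The clocks need not start together. The Synopsis counts from discontinuation of treatment, Protocol 3.2 from the decision to discontinue, and the SAP from treatment discontinuation without defining it as last dose or decision. In Arm B, treatment is given on Days 1 to 5 of a 21-day cycle. A decision taken when the next cycle would start (Day 22) comes 22 − 5 = 17 days after the last dose. The earliest Visit 801 is then 17 + 16 = 33 days after last dose, and a window counted from last dose has no gap. If both clocks start at the decision, the gap can be the full 14 days.

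**2. Missing day set to the 15th**

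- Loss: first dose 20 March, true onset 25 March, day missing. Imputed onset is 15 March, before first dose, so the AE is pre-existing.
- Gain: first dose 10 March, true onset 4 March, day missing. Imputed onset is 15 March, after first dose, so the AE is a TEAE.

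A first dose on the 16th or later loses every onset in that month whose day is missing. Such dates make up 185 of 365 in a non-leap year (51%).

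To size this, take each of the 365 possible first-dose dates as equally likely, place true onsets on each of days 0 to 20 after first dose, delete the day, impute the 15th, and compare with first dose:

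- all first-dose dates: 19.9% of onsets become pre-existing
- first dose on the 16th or later: 39.2%
- true onsets in the 28 days before first dose that become TEAEs: 12.3%

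Where only the year is known, an onset in the year of first dose is set before first dose whenever first dose is after 1 July (183/365 = 50% of dates).

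**3. Death dates**

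A participant last known alive on 20 May who dies later that month, with the day missing, is given a death date of 15 May, five days before the last contact.

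**The case against.** Several points on the other side stand.

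- **Collection narrows; it does not close.** Treatment-related serious events are still reported after Visit 801, survival follow-up continues, and all deaths are tabulated (SAP 7.9.3). A serious, related late infection or cytopenia is not lost.
- **47% is a worst case.** Day 30 is the target, and a footnote to Table JP04.3 describes short-term follow-up as lasting roughly that long. That footnote does not remove the gap, because the reporting rule names the visit. A reader might spread visits evenly over Days 16 to 44 and infer that half of participants have a gap averaging 7 days, or 0.5 × 7 = 3.5 days overall. The documents give no visit-timing data to support that.
- **A difference by arm is not shown.** A reader might infer one, because investigators know the arm when they judge relatedness. That is a possible mechanism, but nothing in the documents establishes a difference in visit timing or reporting.
- **The date rule does not only lose TEAEs.** It also creates them. A lost event returns if its grade rises, registry tables include SAEs whether or not they are TEAEs (SAP 7.14), and laboratory grades come from measured values (SAP 7.9.4).
- **Missing days should be uncommon.** AEs are collected continuously, with frequent visits. No frequency is given.
- **A governing document is unseen.** Protocol 3.9.2 refers AE reporting to the CAMPFIRE Master Protocol, which could require collection to Day 30. Neither document here says that it does.

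These points limit the size of the problem. They do not reconcile the two windows or make the date rule correct as written.

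**Conclusion.** Both points hold as defects in stated rules whose effect cannot be counted from the documents.

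Between an early Visit 801 and Day 30, non-serious AEs and SAEs judged unrelated are not collected, although the SAP counts them. The loss per participant ranges from 0 to 14 of 30 days, assuming that the visit and the TEAE window are counted from the same day. The differing anchors must be reconciled before that range is firm.

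The 15th-of-month rule misclassifies onsets around first dose in both directions: about 20% of day-missing onsets in the first 21 days become pre-existing, and about 12% of day-missing onsets in the 28 days before dosing become TEAEs. Both percentages assume first doses spread evenly over the year, and they apply only to AEs with a missing day. The death-date error is possible under the rule, and its frequency is unknown.

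The documents do not support a claim that AE collection ends at Visit 801, that half of participants are affected, or that the loss favours one arm.

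**What to change.** **Protocol.** In Table JP04.3, collect all AEs until the later of Visit 801 and 30 days after treatment discontinuation, by telephone when the visit is early. Alternatively, set the Visit 801 window to 0 to +14 days wherever it is stated: Synopsis, 3.2, Table JP04.3, and the Germany and Spain sections of Attachment 9. Either change is subject to any rule in the Master Protocol. State one anchor for Visit 801 and use it in the TEAE definition in SAP 7.9.2.

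**SAP 7.1.2.** Add two sentences:

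- An imputed AE onset is not earlier than first dose unless the known parts of the date or the stop date show that it was.
- An imputed death date is not earlier than the day after the participant was last known alive.

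**Cost.** The telephone option costs one short call per early visit. The window option touches more text and moves some visits up to two weeks later.

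The onset limit has its own price. In the same enumeration it cuts the loss from 19.9% to 0%, but raises the share of day-missing onsets in the 28 days before dosing that count as TEAEs from 12.3% to 52.3% when nothing shows whether onset preceded dosing. The known date parts and stop date will reduce that share, and what remains errs toward over-reporting, the cautious direction for safety.
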